**Figure 1 Study flow chart**

**Table 1 Study plan (For more outlined study plans see appendix L)**

Visit Nos.	1	2 	3 	4	5 	6 	7	8	9	10	11	12	13	14	15	16	Ext ra visit	Dis cont. visit 
Week/month Assessments	-12 w	-6 w ±1w	-5 w	0	<3m	<4 m	6m ±2w	12 m ±2w	18 m ±2w	24 m ±2w	30m ±2w	36 m ±2w	42 m ±2w	48 m ±2w	54 m ±2w	60 m ±2w		
Endoscopy incl. biopsies Hp status	X 		X 	X 				X				X				X	X 	X
24 hr pH metry, manometry & SAP 	X 		X 				X									X	X 	X
Surgery 					X													
Post-operative symptoms 						X												
QOLRAD, GSRS				X				X		X		X		X		X		X
Symptoms	X	X	X	X		X	X	X	X	X	X	X	X	X	X	X	X	X
Laboratory screen	X 		X 					X				X				X		X
Medical, surgical hist., demograph.	X																	
Vital signs incl. body weight	X			X 				X 				X 				X 	X 	X 
Inclusion and exclusion criteria	X			X														
Dispense study drug	X			X	X		X 	X 	X 	X 	X 	X 	X 	X 	X 		X 	
Randomization				X														
Compliance			X	X	X	X 	X 	X 	X 	X 	X 	X 	X 	X 	X 	X 	X 	X 
Written Informed consent and Subj. information	X																	
Adverse events 		X	X	X		X	X	X	X	X	X	X	X	X	X	X	X	X

1 If pH monitoring was less than 18 hours, pH metry should be repeated. Manometry should be done by all subjects only on the first occasion of pH metry

- 2 Only for subjects randomized to surgery.
- 3 All SAE and those AE causing premature discontinuation of study drug and/or study.
- 4
- 5 Only for subjects who were untreated with PPI prior to study enrolment and if an appointment for pH metry was scheduled within 2 weeks from visit 1.
- 6 Withholding of medical treatment
- 7 7 days after visit 2
- 8 Only for subjects who were treated with PPI prior to study enrolment or if too few biopsy specimens were taken from untreated subjects at visit 1.
- 9 For all subjects unless pH metry and laboratory screen was done at visit 1 for untreated subjects.
- 10 Only for subjects with RE LA grade C or D at visits 1 or 3.
- 11 Only body weight
- 12 30 days after visit 5 (surgery)
- 13 Only for subjects in the surgical arm receiving esomeprazole
- 14 Only for subjects in the medical arm
- 15 In case of administration of healing dose (esomeprazole 40 mg o.d.)
- 16 In case of dose adjustment
- 17 In case of premature discontinuation after randomization (visit 4)

**Table 2 Study plan prolongation**

Visit Nos.	16 a	30 b	31	32 b	33	34 b	35	36 b	37	38 b	39	Extra visit	Discont. Visit h
Year	5 ±6w	5.5 ±6w	6 ±6w	6.6 ±6w	7 ±6w	7.5 ±6w	8 ±6w	8.5 ±6w	9 ±6w	9.5 ±6w	10 ±6w		17
	X												
Endoscopy incl. biopsies Hp status	X				X						X	X f	X
24 hr pH metry, manometry & SAP c												X g	X
QOLRAD, GSRs	X		X		X		X		X		X		X
Symptoms	X		X		X		X		X		X	X	X
Laboratory screen	X				X						X		X
Body weight	X				X						X	X	X
Dispense study drug d	X		X		X		X		X			X	
Compliance d	X		X		X		X		X		X	X	X
Concomitant Medication	X		X		X		X		X		X	X	X
AE e	X	X	X	X	X	X	X	X	X	X	X	X	X
Informed consent and blood sample for genetic research (optional) i	X												

- a Last Visit in the 5-year LOTUS study
- b Telephone Visit (hospital visit optional)
- c If pH monitoring was less than 18 hours, pH metry should be repeated
- d Only for Subjects in the medical arm
- e All SAE and those AE causing premature discontinuation of study drug and/or study
- f In case of administration of healing dose (esomeprazole 40mg o.d)
- g In case of increased dose
- h In case of premature discontinuation
- i See appendix O

### 3.2 Rationale for study design, doses and control groups

This study is designed to investigate the efficacy and tolerability of long-term treatment with esomeprazole compared to anti-reflux surgery i.e. laparoscopic fundoplication.

The 12-week run-in period allows for the treatment of reflux esophagitis, enables the initial tolerability to esomeprazole to be controlled and allows for the collection of baseline data.

Dose adjustment not exceeding 40 mg daily will be allowed. Esomeprazole 40 mg o.d. has been chosen for during the run-in period. This dose has been shown to be the most effective in the healing of reflux esophagitis (Richter JE et al 2001).

Laparoscopic fundoplication is the surgical method chosen to be the comparator to long-term medical treatment (for surgical details see Section 3.4.2).

The duration of the study is 10 years. The target population is adult subjects with chronic gastroesophageal reflux disease in need for either long-term medical treatment or surgical treatment. All subjects should be eligible for surgery. The subjects will be randomized to either medical treatment or anti-reflux surgery.

### **3.2.1 Risk/benefit and ethical assessment**

The prolongation is a an additional 5-year follow-up of a 5-year comparison between esomeprazole and laparoscopic reflux surgery in patients with severe GERD.

The subjects health will be monitored during regular visits to the investigator. There have not been any findings in the ongoing study that indicate any safety concerns.

In the prolongation the subjects will be followed up with regular visits to the investigator. The benefit to the patient is mainly the possibility of regular long term health/therapy controls of a life-long severe disease with risk for complications

## **3.3 Selection of study population**

### **3.3.1 Study selection record**

The investigator must keep a record of subjects who were considered for enrolment but never enrolled. This information is necessary to establish that the patient population was selected without bias. This record will be kept at the centre and will not be entered into any database at AstraZeneca.

### **3.3.2 Inclusion criteria (at enrolment)**

For inclusion in the study subjects must fulfil all of the following criteria:

1. Provision of written informed consent
2. Male or female 18-70 years of age.
3. Ability to complete the Quality of Life questionnaires
4. Subjects with a history of chronic (> 6 months) reflux esophagitis (endoscopically verified) or a history of chronic (> 6 months) symptomatic GERD with pathological

24 hour pH metry according to local standards and in need for long-term treatment with acid suppressive therapy.

5. Subjects considered suitable for surgical treatment and long-term management with esomeprazole.

### 3.3.3 Inclusion criteria (at randomization)

For randomization in the study subjects must fulfil all of the following criteria

6. Subjects considered suitable for surgical treatment and long-term management with esomeprazole.
7. None or mild symptoms of GERD at the end of the run-in period.
8. Subjects should not have more than LA grade B endoscopic-visualized mucosal breaks at the last endoscopy prior to randomization.

### 3.3.4 Exclusion criteria

Any of the following is regarded as a criterion for exclusion from the study:

1. History of esophageal, gastric or duodenal surgery predicted to influence negatively on subsequent treatment within the study.
2. Subjects with **current** or **historical** evidence of the following diseases/conditions:
  - Zollinger-Ellison syndrome
  - The primary esophageal disorders; achalasia, scleroderma and primary esophageal spasms
  - Inflammatory bowel disease.
  - Dysplastic changes in a columnar lined esophagus.
  - Any condition associated with abnormal absorption in the GI tract.
  - Significant cardiovascular, pulmonary, pancreatic, renal or liver diseases as judged by the investigator to interfere with the evaluation of the study.
  - Malignant disease except of minor superficial skin disease.
  - Current unstable diabetes mellitus. Stable diabetics controlled on diet, oral agents or insulin are acceptable.
  - Cerebral vascular disease, such as cerebral ischemia, infarction, haemorrhage or embolus as judged by the investigator.

3. Contraindication to the study drug, e.g. known or suspected allergy to esomeprazole and any other constituents of the formulation. Known hypersensitivity to substituted benzimidazole.
4. Pregnancy or lactation.
5. Child-bearing potential (female subjects must be post-menopausal, surgically sterilized or using medically accepted contraceptive measures during the study period as judged by the investigator).
6. Any significant “alarm symptoms” such as unintentional weight loss, recurrent vomiting, recurrent dysphagia, anaemia, haematemesis, melaena, jaundice or any other sign indicating serious or malignant disease.
7. Need for concomitant therapy with:
  - per oral anticholinergics and other drugs having anticholinergic co-effects such as tricyclic and tetracyclic antidepressive drugs
  - motility activators (prokinetic drugs) – except for operated subjects between visit 5 and visit 6 for treatment of post-operative intestinal paralysis.
  - prostaglandin analogues
  - NSAIDs (except for intermittent usage)
  - ASA (except for 165 mg daily or less for cardiovascular prophylaxis and for intermittent usage)
  - anticoagulants
  - PPI (other than study medication),
  - H2RA
8. Use of any other investigational compound or participation in another clinical trial within 28 days prior to entry of the study.
9. Previous participation in this study.
10. Alcohol and/or drug abuse or any condition associated with poor compliance, including expected non-cooperation, as judged by the investigator.
11. Requirement of an interpreter.

### **3.3.5 Discontinuation of subjects from treatment or assessment**

#### **3.3.5.1 Criteria for discontinuation**

Subjects may be discontinued from study treatment and assessments at any time, at the discretion of the investigator(s). A subject may, however, continue the study under exceptional circumstances (e.g. if continuation of study treatment or follow-up actions are necessary for the subjects safety and well-being, and the continuation of the study is not expected to be associated with any risk or discomfort for the subject). Specific reasons for discontinuing a subject from this study are:

1. Withdrawal of informed consent
2. Unwillingness to continue the study or lost to follow-up.
3. Any unacceptable adverse event, including laboratory result or physical findings, as judged by the investigator
4. Any “alarm symptoms” which, in the investigator’s judgement, requires treatment outside this protocol.
5. Continuous need for/intake of drugs listed under Section [3.3.4](#) criteria 7.
6. Protocol non-compliance as judged by the investigator
7. Classified as treatment failure
8. Pregnancy
9. Incorrect enrolment or randomization of subject
10. Other reason specified by the investigator.

#### **3.3.5.2 Voluntary discontinuation by a subject**

Subjects are free to discontinue their participation in the study at any time, without prejudice to further treatment. Subjects who discontinue from the study should always be asked about the reason(s) for their discontinuation and about the presence of any adverse events. If possible, they should be seen and assessed by an investigator(s). Adverse events should be followed up, questionnaires (e.g., for PRO assessments) and investigational products should be returned by the subject.

#### **3.3.5.3 Incorrectly enrolled or randomized subjects**

Incorrectly enrolled or randomized subjects will be discontinued from further study treatment and assessments.

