### **3.4.2 Doses and treatment regimens**

The medication arm of the study design includes the following:

- esomeprazole
- oral administration
- the start dose is 20 mg once daily and may be adjusted not to exceed 40 mg total daily dose and be swallowed together with a glass of water.

The surgical arm of the study design includes the following:

The surgical procedure is laparoscopic fundoplication. The surgical procedure to be used is laparoscopic total fundoplication and reconstruction of the hiatus. A per-operative record should be filled in and sent by the monitor to AstraZeneca R&D Mölndal for datahandling. The procedure should be done by or supervised by an experienced surgeon. Surgery should be performed within three months of randomization. The subject is allowed to be treated with esomeprazole 20 mg o.d or 40 mg o.d awaiting the surgery.

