### **3.4.3 Method of assigning subjects to treatment groups**

Individual treatment codes, indicating the treatment allocation for each randomized subject, will be provided by AstraZeneca.

The subjects will be randomized into either esomeprazole or anti-reflux surgery.

Subject eligibility will be established before treatment randomization. Subjects will be randomized strictly sequentially. If a subject discontinues from the study, the randomization number will not be reused, and the subject will not be allowed to re-enter the study.

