### **3.4.4 Blinding and procedures for breaking the blind**

#### **3.4.4.1 Methods for ensuring blinding**

Not applicable, as this is an open study. See Section [3.2](#).

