### **6.2 Statistical evaluation**

#### **6.2.1 Methods of statistical analysis**

A comprehensive Statistical Analysis Plan will be prepared before unblinding the data, or in instances where the data are not blinded, database lock.

Both Intention To Treat (ITT) and Per Protocol (PP) analyses will be made for the primary variable. Secondary variables will be analysed for the ITT population only. In the ITT analyses all randomized subjects will be included, except subjects who are randomized into medical treatment and who have taken no dose of study drug, or subjects who are randomized to laparoscopic fundoplication and who refuse to undergo the operation. The PP population will include subjects with no major protocol violations, including the violation of entry criteria (the nature and reasons for these protocol violations will be defined and documented before

database lock). Subjects eligible for safety evaluation are those who take at least one dose of the study drug and for whom post-dose information is available.

The two treatment groups will be compared regarding the primary endpoint using Life Table methods for graphic presentation and a logrank test for statistical inference.

For each GSRS and QOLRAD dimension, the individual score at each assessment is calculated as the average score for the items included in the dimension. If there are missing items in the questionnaires, the mean of the completed items in one dimension will be imputed to substitute the missing item provided that more than 50% of the items in one dimension are completed.

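### Stopping assessments for randomised subjects later found ineligible causes censoring that may be informative and arm-dependent in an open trial; the size is unknown and may be small

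*Protocol*

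**What the plan says.** Section 3.3.5.3 reads: "Incorrectly enrolled or randomized subjects will be discontinued from further study treatment and assessments". The same event is reason 9 in Section 3.3.5.1: "Incorrect enrolment or randomization of subject". That section has a general exception, "A subject may, however, continue the study under exceptional circumstances", and its examples concern the subject's safety and well-being.

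Section 6.2.1 defines the analysis sets. For ITT: "In the ITT analyses all randomized subjects will be included, except subjects who are randomized into medical treatment and who have taken no dose". A second exception covers surgical subjects who refuse the operation. Ineligibility is not among the exceptions. For PP: "The PP population will include subjects with no major protocol violations, including the violation of entry criteria".

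Section 6.2.3 censors, in both sets, any discontinuation that is not a treatment failure. Section 4.3.2.1 counts time from the start of treatment after randomisation to failure or, failing that, to the last study visit.

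On timing and masking, Section 3.4.3 says "Subject eligibility will be established before treatment randomization", Section 3.4.4.1 says of blinding "Not applicable, as this is an open study", and Section 3.4.2 says "Surgery should be performed within three months of randomization".

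Two further provisions bear on the point. Section 3.3.5.4 asks for a clinic visit with assessments at or soon after discontinuation. Section 3.1 provides telephone calls at 5 and 10 years to discontinued subjects who have not withdrawn consent.

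**The concern.** An ITT comparison relies on following randomised subjects whether or not they later prove to have met the entry criteria. Here the conduct rule and the analysis rule pull apart: Section 6.2.1 keeps the treated violator in ITT, while Section 3.3.5.3 stops the collection of that subject's outcome. ITT then holds the subject only up to the day the breach is found.

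This matters more because the arm is known. Several entry criteria rest on judgement, such as suitability for surgery and the significance of cardiovascular or pulmonary disease. A surgical subject can spend up to 3 months between allocation and treatment, and the medical arm has no matching interval. If breaches came to light more often in one arm, and if the subjects concerned had a different prognosis, the logrank comparison would be distorted. This is a rule of conduct: an analysis plan cannot restore visits that were never made.

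**Working it through.** **1. Follow an incorrectly randomised subject through the text.**

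- *Found after treatment has started.* In ITT (6.2.1); assessments stop (3.3.5.3); censored at discontinuation (6.2.3). Failures before that day count and later ones do not. In PP, a major violator is excluded altogether.
- *Medical subject found before the first dose.* Outside ITT under the no-dose exception (6.2.1).
- *Surgical subject withdrawn by the investigator before the operation.* Section 6.2.1 excludes only those who refuse surgery, so this subject is not excluded by its wording. Section 4.3.2.1 starts the clock at treatment, so no surgical time accrues. The subject's status is undefined.

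**2. What is still collected.** The discontinuation visit (3.3.5.4) is a single assessment. The 5- and 10-year calls (3.1) ask about GERD surgery, present medication and present symptoms, and do not enter the endpoint as defined in 4.3.2.1 and 6.2.3. Both provisions also sit awkwardly with the absolute wording of 3.3.5.3.

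**3. Reproduce the planned precision (6.1).** Inputs: 275 per arm, 70% success in both arms, 95% confidence.

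Half-width = 1.96 × √(2 × 0.70 × 0.30 / 275) = 7.66 points. Adding a continuity correction of 1/275 gives 8.02. Both agree with the stated 8 points.

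**4. Possible shift.** The protocol gives no rate of incorrect randomisation, so everything here is assumed. Let a share *d* of one arm be lost with none lost in the other, let those lost have 5-year failure probability *f*, and let overall failure be 30% in both arms. In a binary 5-year approximation:

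Shift = 0.30 − (0.30 − *d f*)/(1 − *d*)

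Example: *d* = 0.05, *f* = 1 gives 0.30 − 0.25/0.95 = 0.0368. Type I error is from a normal approximation with 275 and 275(1 − *d*) subjects.

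| Lost from one arm | *f* = 30% | *f* = 60% | *f* = 100% |
|---|---|---|---|
| 2% (about 6) | 0; 0.050 | 0.61 points; 0.053 | 1.43 points; 0.066 |
| 5% (about 14) | 0; 0.050 | 1.58 points; 0.069 | 3.68 points; 0.158 |
| 10% (about 28) | 0; 0.050 | 3.33 points; 0.135 | 7.78 points; 0.53 |

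Each cell gives the shift, then the type I error. The last column is an upper bound for its row. The model deletes subjects from time zero, which corresponds to discovery at the very start. Later discovery keeps the failures seen before it, so the shift is smaller for the same subjects.

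**5. Precision.** Loss from one arm of 2%, 5% or 10% widens the half-width only from 7.66 to 7.70, 7.76 or 7.87 points. The issue is bias, not precision.

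**The case against.** The strongest reply is that the route to imbalance is not in the document. A reader might infer an eligibility re-check after open allocation, perhaps during a pre-operative work-up. The protocol describes neither: Section 3.4.3 places eligibility before randomisation, Table 1 schedules the criteria check at visits 1 and 4 only, and visit 5 lists surgery, drug dispensing and compliance. The judgement-based criteria apply to both arms. This stands: unequal discovery is possible but not shown.

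A reader might also infer that these subjects are removed from ITT, or lost to every further assessment. Neither is supported. Treated violators remain in ITT until censored, and the discontinuation visit and telephone calls exist.

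The magnitude is assumption throughout. Cardiovascular or cerebral vascular disease has no stated link to failure of reflux control, and with average prognosis the shift is zero. This also stands.

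Finally, Section 3.3.5.1 lets the investigator discontinue subjects for several other reasons, all censored under 6.2.3, and a subject withdrawn before surgery is not reached by changing 3.3.5.3 alone. That is correct, and it shapes the fix.

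None of this answers the core point. The rule is categorical and covers randomised subjects. The exception in 3.3.5.1 is for exceptional circumstances, and its examples do not include keeping the randomised comparison complete.

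**Conclusion.** The point holds as a conflict between conduct and analysis. Section 3.3.5.3 and reason 9 in 3.3.5.1 end the follow-up of randomised subjects whom 6.2.1 keeps in ITT, and 6.2.3 censors them. In an open trial with up to 3 months' wait in one arm, that censoring may be informative and may depend on the arm.

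Its size cannot be known from the protocol and may be small: zero with average prognosis, 1.6 points if 5% of one arm are lost and would fail at 60%, and about 3.7 points if that 5% would all have failed. These figures assume one-sided loss at the outset and 30% failure overall. They are a range of what could happen, not an estimate, and the documents do not support saying that either arm is in fact selectively depleted. The change is worth making because it is cheap and uncollected outcomes cannot be recovered.

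**What to change.** - In Section 3.3.5.3, remove the stop on assessments for randomised subjects. State that a breach found after randomisation does not in itself end scheduled visits or the treatment-failure questions. Amend reason 9 in 3.3.5.1 to match.
- State in 6.2.1 that such subjects stay in ITT with their observed outcomes and that the breach is handled by PP exclusion. Align the censoring rule in 6.2.3.
- State in 4.3.2.1 and 6.2.1 how a surgical subject withdrawn by the investigator before the operation is counted, including when that subject's time starts. Without this, continued visits give no defined failure time in that case.
- Reconcile 3.3.5.3 with the telephone follow-up in 3.1 and the discontinuation procedures in 3.3.5.4.

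Whether study treatment continues in a subject found ineligible is a separate matter for the sponsor and investigator, and this change should leave it untouched.

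The cost is amendment wording and a few more subjects kept in visits already scheduled. The change does not reach censoring from the other discontinuation reasons in 3.3.5.1.

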### **3.3.5.4 Procedures for discontinuation**

The subject should return for a clinic visit at the time of, or soon after discontinuation with maintained medication (medical arm) for the following assessments:

#### **Discontinuation before randomization:**

- All SAE and those AE causing premature discontinuation of study drug and/or study
- The reason for discontinuation

#### **Discontinuation after randomization:**

- Endoscopy including biopsies and *Hp* status
- Laboratory screening
- Body weight
- All SAE and those AE causing premature discontinuation of study drug and/or study
- Patient reported outcomes
- Symptoms
- 24 hour pH metry and SAP
- The reason for discontinuation

#### **Procedures for discontinuation from genetic aspects of the study**

See Appendix O for description of procedures for discontinuation from the genetic part of the Clinical Study.

After completion or discontinuation of the study the subjects will be treated according to clinical practise for GERD.

